5.1.1 Procedures for randomization

The TRIP study will be a randomized, assessor-blind, active comparator-controlled, clinical trial using a 2×2 factorial design, with 1:1 patient allocation to ticagrelor or clopidogrel and within each treatment a 1:1 allocation to RIPC or control. Patient randomization in the ticagrelor and the clopidogrel group will take place using sealed, opaque envelopes containing a computer-generated randomization scheme. Using a similar procedure, patients will be randomly assigned to RIPC or no RIPC within 1 hour before the procedure.

5.2 Procedures for handling subjects incorrectly enrolled or randomized or initiated on investigational product

Subjects who fail to meet the inclusion and exclusion criteria are defined as screening failures. The investigator will maintain a Screening Log which includes screen failures. The log will document the subject number, subject initials, demographics and the reason(s) for excluding the patient from the study. This log will be kept in the Investigator's Study File. It will be used to determine systematic bias in selection of patients for entry into the study.

Subjects who withdraw or are withdrawn from the study following randomization, before investigational product initiation should:

- Have the reason(s) for their withdrawal recorded

Subjects who withdraw or are withdrawn from the study following randomization and investigational product initiation should:

- Have the reason(s) for their withdrawal recorded
- Be asked about the presence of any AEs and if so should be followed up by regular scheduled visits, telephone contact, correspondence or home visits until satisfactory clinical resolution of AEs is achieved.
- Be seen by an investigator and all final assessments will be performed and recorded in the termination page of CRF.
- Have at least one follow-up contact for safety evaluation during the 30 days following the last dose of study treatment.
- In the event of pregnancy, the subject should be monitored until conclusion of the pregnancy and the outcome of pregnancy reported.
- Have study treatment returned (according to accountability practices)

5.3 Blinding and procedures for unblinding the study

The TRIP study will be an open label study with a blinded assessor. Accordingly, two investigators unaware of the patients' allocation will assess outcomes. In detail, each study patient will have a post-procedural cTnI measurement and a pain measurement not amenable to assessment; however the ST-segment deviation will be decided by two blinded expert investigators. In the event of discrepant assessments, final outcome will be defined by consensus between the two assessors.

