3.2 Rationale for study design, doses and control groups

Patients allocated to RIPC will undergo a RIPC protocol within 60 minutes prior to PCI, according to previously established preconditioning protocols (CRISP stent study).²¹ Antiplatelet doses in the ticagrelor and the control group are according to established practice guidelines (ESC Guidelines for Revascularization 2014).²³

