5. STUDY CONDUCT

5.1 Subject enrollment, randomization, and initiation of investigational product

According to the study protocol, patients who are referred for coronary angiography or NSTEMI-ACS may be screened for randomization. Subjects meeting the inclusion and none of the exclusion criteria will be evaluated and their demographic, medical history and current clinical characteristics will be recorded.

During the screening period the eligibility check and physical examination will be performed with assessment of vital signs (heart rate and blood pressure measurement). During the screening period obtained local laboratory results should be examined for exclusion criteria (eGFR, HAS-BLED score, cardiac troponin). The subject will then be informed about the study and will sign the Informed Consent Form.

Day 1 of the study is defined as the day of randomization to ticagrelor versus clopidogrel. This should be chosen by the investigator to be the day before the scheduled PCI procedure.

Day 2 of the study is defined as the day of randomization to RIPC or control and subsequent (within 1 hour) coronary angiography and PCI.

In patients already treated with clopidogrel for 3 to 7 days, actions performed on Day 1 and Day 2 may be combined into a single day provided that;

- a. Twenty-four hours have elapsed between the last dose of clopidogrel and the randomization to the ticagrelor or clopidogrel group, and
- b. There is sufficient time (2-4 hours) between the randomization and subsequent intake of clopidogrel or ticagrelor and the 2nd randomization to the RIPC or control group.

In these case patients are 1:1 randomized to ticagrelor or clopidogrel, and undergo the second randomization within 2-4 hours

If for unforeseen reasons, PCI is not conducted within the prespecified timeframe the patient should be withdrawn from the study.

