6.2 Data collection at enrolment and follow-up

Screening (in most cases expected to be the same day with first randomization-Day1)

During this period the investigator will evaluate and record

- Indication for coronary angiography or PCI (stable CAD, NSTEMI-ACS)
- Demographics (age, gender, height, weight, body mass index)
- History of risk factors for cardiovascular disease (Diabetes mellitus, dyslipidemia, hypertension, smoking)
- Medical history including history of previous MI, previous PCI, previous CABG, New York Heart Association Class, Canadian Cardiology Society Angina Class
- Prior and concomitant medication
- Physical examination with vital signs (heart rate, blood pressure)
- Electrocardiogram
- Local laboratory values (hemoglobin, complete blood count including platelet count, serum creatinine, AST, ALT, INR, cardiac Troponin I)

Day 2 - Pre-procedural assessment

- Physical examination with vital signs (heart rate, blood pressure). At this time signs and symptoms of bleeding should be specifically examined.
- Local laboratory values (hemoglobin, complete blood count including platelet count, serum creatinine, AST, ALT, INR, cardiac Troponin I)

In the case of patients already on clopidogrel there will be one combined assessment for screening and pre-procedurally.

Day 2 - Preconditioning

- The timing of the last cycle of RIPC in relation to subsequent PCI should be specifically recorded

Day 2 - Peri-procedural

- Angiographic parameters (number of diseased vessels, target vessel, jeopardy score, rentrop score, American heart association lesion type, stenosis severity, acute gain, timi flow score)
- Procedural parameters (access site, stent length, type of stent used, screen time, radiation dose, contrast dose, number of predilations, predilation time, number of postdilations, postdilation time)
- Complications (jailed side branch, dissection)
- ST-segment deviation during balloon occlusion will be monitored as a secondary efficacy variable. It will be defined as the absolute value of ST-segment deviation at 60-80ms after the J-point in mm at the beginning of coronary angiography minus ST-segment deviation at 60-80ms after the J-point in mm during balloon occlusion.

Day 2 - Post-procedural

- Physical examination with vital signs (heart rate, blood pressure). At this time signs and symptoms of access site bleeding should be specifically examined.
- Electrocardiogram

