6.3 Efficacy

6.3.1 Efficacy variables

The primary efficacy variable, cardiac troponin I at 24 hours post-PCI will be determined according to local standard clinical practice. In detail, cTnI will be analyzed with an automated immunoassay (Bayer ADVIA IMS Troponin-I Ultra method, Bayer, Berlin, Germany). The 99th percentile of the cTnI level in a reference population (upper reference limit, URL) of healthy volunteers was below the lower limit of detection of 0.04 ng/mL. The coefficient of variation (CV) of the assay was <10%, complying with the recommendations of the European Society of Cardiology (ESC)/ American College of Cardiology (ACC)/ American Heart Association (AHA) for optimal precision. The analytical range was 0.01 to 50ng/mL, with an assay sensitivity of 0.006 ng/mL.

Chest pain during PCI is a secondary efficacy variable. It will be assessed during the post-PCI clinical examination of the subject by the investigator or by an appropriately qualified person to whom the investigator has delegated this duty. An analog 10 point scale will be used (0: no pain, 10: most severe discomfort ever experienced).

ST-segment deviation during balloon occlusion will be monitored as a secondary efficacy variable. It will be defined as the absolute value of ST-segment deviation at 60-80ms after the J-point in mm at the beginning of coronary angiography minus ST-segment deviation at 60-80ms after the J-point in mm during balloon occlusion.

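### Nothing keeps the RIPC allocation from the PCI operator, which exposes the RIPC main effect and the ticagrelor-RIPC versus ticagrelor-alone comparison to performance bias and allocation-dependent withdrawal

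*Combined protocol and SAP*

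**What the plan says.** Section 5.3 sets the blinding: "The TRIP study will be an open label study with a blinded assessor". It says that two investigators unaware of allocation assess outcomes, then narrows what they do. On cTnI and pain it says that "each study patient will have a post-procedural cTnI measurement and a pain measurement not amenable to assessment". The remaining variable is the one they handle: "however the ST-segment deviation will be decided by two blinded expert investigators". Section 6.3.1 has pain assessed "by the investigator or by an appropriately qualified person to whom the investigator has delegated this duty", with no blinding condition.

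On timing, Section 5.1.1 says "patients will be randomly assigned to RIPC or no RIPC within 1 hour before the procedure", and Section 5.1 defines Day 2 by "randomization to RIPC or control and subsequent (within 1 hour) coronary angiography and PCI". Section 3.2 confirms the order: "Patients allocated to RIPC will undergo a RIPC protocol within 60 minutes prior to PCI". Section 5.1 also withdraws any patient whose PCI is not done in the planned window.

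Section 6.2 records procedural details that include "number of predilations, predilation time, number of postdilations, postdilation time". No section standardises them.

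Section 12.1.1 requires RIPC or a sham procedure for the per-protocol set. No other section mentions or describes a sham.

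**The concern.** The automated cTnI assay and the blinded ST readers protect the measurement of those outcomes. They do not protect the conduct of the procedure that produces the injury. An operator who knows whether the patient was preconditioned may, without intending it, inflate for longer or shorter, post-dilate more or less, or be more or less ready to go ahead after the angiogram.

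There are two consequences. First, mean cTnI and ST deviation could differ between RIPC and control for a reason other than RIPC. Second, loss after randomisation could depend on allocation. A patient without PCI has no 24-hour post-PCI cTnI and so cannot contribute to the primary analysis, whichever analysis set is used.

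The ANCOVA in Section 12.2 adjusts only for pre-procedural cTnI. The recorded inflation data could show that practice differed between arms. They arise after allocation, so adjusting for them would not be a simple repair.

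**Working it through.** **Who can know the RIPC allocation, and when**

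| Step | Section | Blinding stated |
|---|---|---|
| RIPC envelope opened | 5.1.1 | none; person not named |
| RIPC or control given | 3.2, 5.1 | none |
| Angiogram and decision to proceed | 5.1 | none |
| Balloon inflations | 6.2 | none |
| Reading of ST deviation | 5.3 | two blinded readers |
| cTnI at 24 h | 6.3.1 | automated assay |
| Pain score | 6.3.1, 6.5 | none |

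The link from inflation to outcome is in the plan itself. Section 1.1 attributes the proximal type of injury mainly to side branch occlusion during inflation or stenting. Sections 6.3.1 and 6.5 tie ST deviation and pain to balloon occlusion.

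**Inputs from Section 12.3**

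SD 0.20 ng/mL; pre/post correlation 0.7; N = 152; dropout 15%; two-sided alpha 0.05. Cell means (ng/mL): ticagrelor-RIPC 0.08, clopidogrel-RIPC 0.12, ticagrelor-control 0.14, clopidogrel-control 0.24.

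**The plan's own figure**

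- Covariate-adjusted SD = 0.20 × √(1 − 0.7²) = 0.1428.
- Drug main effect = (0.12 + 0.24)/2 − (0.08 + 0.14)/2 = 0.07.
- n per margin = 2 × (1.960 + 0.842)² × 0.1428² / 0.07² = 65.4, so 66, or 132 in total.
- 132 × 1.15 = 151.8, so 152. The stated total is reproduced, and these inputs can be used below.

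**Illustration for the RIPC main effect**

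The shift b is an assumption; the documents give no value for it.

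- Evaluable patients = 152 × 0.85 = 129.2.
- SE = 0.1428 × √(4/129.2) = 0.0251 ng/mL.
- Planned effect = 0.19 − 0.10 = 0.09 ng/mL.
- No true effect, shift b away from the null: error = 1 − Φ(1.96 − b/SE) + Φ(−1.96 − b/SE).
- True effect 0.09, shift b towards the null: power = Φ((0.09 − b)/SE − 1.96).

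| b (ng/mL) | Share of 0.09 | Two-sided error | Power if towards the null |
|---|---|---|---|
| 0 | 0% | 5% | 95% |
| 0.01 | 11% | 6.8% | 89% |
| 0.02 | 22% | 12.5% | 80% |
| 0.03 | 33% | 22.3% | 67% |

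**Illustration for ticagrelor-RIPC versus ticagrelor alone**

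This comparison is named in the primary objective (Section 2.1).

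- Planned difference = 0.14 − 0.08 = 0.06 ng/mL.
- SE with 129.2/4 = 32.3 per cell = 0.1428 × √(2/32.3) = 0.0355 ng/mL.
- Shifts of 0.01, 0.02 and 0.03 are 17%, 33% and 50% of the planned difference. By the same formula they raise the error to 5.9%, 8.7% and 13.5%. The inflation is smaller than for the main effect because the standard error is larger.

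**Ticagrelor-RIPC versus clopidogrel-RIPC**

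Both cells receive RIPC, so knowing the RIPC allocation does not separate them.

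**The case against.** The strongest reply is that this is a declared design. The plan consistently describes an assessor-blind trial, the primary outcome is an automated assay, and the one efficacy variable that needs interpretation has two blinded readers. The documents do not say who opens the envelope or applies the cuff, so they do not show that the operator does know the allocation. That stands: the point is that nothing prevents it. Declaring the design does not remove performance bias.

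A reader might infer that operator technique drives all three efficacy variables. The documents do not support that. Section 1.1 puts 50–75% of cases in the distal type, through embolism, platelet activation, microvascular plugging and inflammation, and does not describe these as operator-driven. It traces even side branch occlusion to plaque shift, thrombus or dissection. Inflation practice can contribute to cTnI release; the plan does not make it the main cause.

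A reader might also take the error rates above as an estimate of bias. They are not. Neither size nor direction can be obtained from the documents. If operators were gentler with unprotected patients, the effect would be diluted and power lost.

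The sham procedure in Section 12.1.1 suggests that some concealment may have been intended. It is undefined, sits badly with the open-label statement in Section 5.3 and the no-RIPC comparator in Section 5.1.1, and would conceal RIPC from the patient rather than from the operator.

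Partial safeguards deserve credit. Inflations, jailed side branches and dissections are recorded, reasons for withdrawal are recorded, and patients are selected as eligible for PCI. These help to detect a problem and narrow the operator's discretion, but they do not prevent bias.

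**Conclusion.** The concern holds in limited form. As written, the plan lets the operator know the RIPC allocation before deciding on PCI and choosing inflations. The RIPC main effect and the ticagrelor-RIPC versus ticagrelor-alone comparison are therefore open to performance bias and to withdrawal that depends on allocation. The other comparison in the primary objective is not affected by this route. Open drug allocation is a separate exposure that this point does not address.

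The illustration (about 7%, 13% and 22% error on the RIPC main effect) rests on the planning SD and correlation, 15% loss, and shifts chosen for the purpose. It shows only that a shift of about a fifth of the planned RIPC effect would matter if it ran away from the null. It is not evidence that such a shift will occur.

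The change is worth making because it is cheap. That staff other than the operator are available is a design judgement: RIPC is given before PCI, which makes it plausible, but the documents do not describe staffing.

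**What to change.** In Sections 5.1.1 and 5.3, state that:

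- existing site staff other than the PCI operator open the RIPC envelope and apply and remove the cuff, out of the operator's sight;
- those staff record the time of the last RIPC cycle, which Section 6.2 already requires;
- the operator is not told the RIPC allocation until the 24-hour cTnI sample is drawn, unless patient care requires it;
- any unblinding of the operator is recorded.

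Reconcile the no-RIPC comparator in Section 5.1.1, the open-label statement in Section 5.3 and the sham procedure in Section 12.1.1. Either describe the sham and say who is blinded by it, or remove it from the per-protocol definition.

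The sample size, visits and drug regimens do not change. The cost is some coordination on the day of PCI. An awake patient who knows the allocation will sometimes disclose it. Patient-reported pain is not protected by this change unless a sham is actually used.

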2.3 Safety objective

Safety monitoring will be performed daily during the index hospitalization. The presence of adverse events will be assessed by history, detailed physical examination and appropriate laboratory tests that will be described in the protocol accordingly.

In addition patients will be instructed to contact the study personnel in case of any emergency situation whereas an adverse event reporting system will be available throughout the study.

In detail, bleeding according to the Thrombolysis in Myocardial Infarction (TIMI) bleeding criteria will be recorded and assessed throughout study duration. According to these criteria bleeding is defined as follows:

Non-CABG Related Bleeding:

1. Major

- Any intracranial bleeding (excluding microhemorrhages <10 mm evident only on gradient-echo MRI)
- Clinically overt signs of hemorrhage associated with a drop in hemoglobin of ≥ 5 g/dL or a $\geq 15\%$ absolute decrease in haematocrit
- Fatal bleeding (bleeding that directly results in death within 7 d)

2. Minor

- Clinically overt (including imaging), resulting in hemoglobin drop of 3 to <5 g/dL or $\geq 10\%$ decrease in haematocrit
- No observed blood loss: ≥ 4 g/dL decrease in the haemoglobin concentration or $\geq 12\%$ decrease in haematocrit

- Any overt sign of hemorrhage that meets one of the following criteria and does not meet criteria for a major or minor bleeding event, as defined above
- Requiring intervention (medical practitioner-guided medical or surgical treatment to stop or treat bleeding, including temporarily or permanently discontinuing or changing the dose of a medication or study drug)
- Leading to or prolonging hospitalization
- Prompting evaluation (leading to an unscheduled visit to a healthcare professional and diagnostic testing, either laboratory or imaging)

3. Minimal

- Any overt bleeding event that does not meet the criteria above
- Any clinically overt sign of haemorrhage (including imaging) associated with a <3 g/dL decrease in haemoglobin concentration or <9% decrease in haematocrit

Bleeding in the Setting of CABG:

- Fatal bleeding (bleeding that directly results in death)
- Perioperative intracranial bleeding
- Reoperation after closure of the sternotomy incision for the purpose of controlling bleeding
- Transfusion of ≥ 5 U PRBCs or whole blood within a 48-h period; cell saver transfusion will not be counted in calculations of blood products.
- Chest tube output >2 L within a 24-h period

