11.2 Calculation or derivation of safety variable(s)

The frequency of bleeding according the TIMI criteria will be recorded.

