12.2 Methods of statistical analyses

The efficacy analysis will be performed in the population of subjects valid for safety analysis.

The statistical assessment of the primary outcome measure (post-procedural cTnI) will be performed using ANCOVA (analysis of covariance), with post-procedural cTnI as a dependent variable, -ticagrelor/clopidogrel treatment and –RIPC/no RIPC as fixed factors and pre-procedural cTnI as a covariate. If not mentioned otherwise, all statistical tests will be performed tow-sided with a type I error rate of 5% and 95% confidence intervals (two-sided) will be given.

The statistical assessment of the secondary outcome measures (pain score, and ST-segment deviation) will be performed using ANOVA (analysis of variance). The ANOVA tests the null hypothesis that samples in two or more groups are drawn from populations with the same mean values. If the ANOVA test is statistically significant, pairwise comparison of subgroups will be performed with the Tukey-Kramer test. If not mentioned otherwise, all statistical tests will be performed tow-sided with a type I error rate of 5% and 95% confidence intervals (two-sided) will be given.

The safety analysis will be performed in the population of subjects valid for safety analysis.

The incidence of the composite of major and non-major bleeding according to the TIMI criteria and the incidence of major bleeding will be tabulated and further analyzed using Fisher's exact test. Fisher's exact test is a significance test for a 2x2 table. This test evaluates all distribution probabilities for a 2 x 2 table and produces an exact probability for a given set of observed frequencies. The null hypothesis is that the row and column variables are unrelated, or that there is no difference in the respective proportions. If not mentioned otherwise, all statistical tests will be performed two-sided with a type I error rate of 5% and 95% confidence intervals (two-sided) will be given.

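### Blinded assessment is spelled out for ST-segment deviation only; TIMI bleeding, the only safety outcome with planned tests, has no stated grader and no masked review

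*Combined protocol and SAP*

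**What the plan says.** Section 5.3 sets the blinding: "The TRIP study will be an open label study with a blinded assessor". It continues in general terms that "two investigators unaware of the patients' allocation will assess outcomes". The detail that follows covers three variables. On troponin and pain it says that "each study patient will have a post-procedural cTnI measurement and a pain measurement not amenable to assessment"; on the third, "however the ST-segment deviation will be decided by two blinded expert investigators". Disagreements between the two assessors go to consensus. Bleeding is not mentioned in 5.3.

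Section 2.3 defines the TIMI classes and has bleeding followed throughout the study. Section 11.2 says only this about derivation: "The frequency of bleeding according the TIMI criteria will be recorded". Sections 6.2 and 6.4.8 provide bleeding-directed physical examinations. After discharge, patients are told to report adverse events to the investigator, and there is a Day 30 visit. Scheduled haemoglobin tests fall on Days 1, 2 and 3 only (6.4.4).

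Section 12.2 names what is tested by Fisher's exact test: "The incidence of the composite of major and non-major bleeding according to the TIMI criteria and the incidence of major bleeding". No other safety variable has a planned test.

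**The concern.** Sections 3.1 and 5.1.1 call the trial assessor-blind, and a reader will assume that this extends to the one safety outcome that is formally tested. On the text it does not clearly do so.

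Section 1.4 records an expectation of more bleeding with the more potent drug, so anyone classifying bleeds with knowledge of the arm has a prior view. Several items in 2.3 call for judgement: whether a sign is clinically overt, and the catch-all minimal item, "Any overt bleeding event that does not meet the criteria above". At stake is the credibility of the ticagrelor-versus-clopidogrel bleeding comparison, which is the risk side of the benefit-risk argument in 1.4. Bias could run either way: a site might class ticagrelor events higher because it expects them, or dismiss them as expected.

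**Working it through.** The plan gives no bleeding rate and no power figure for bleeding, so there is no stated figure to reproduce. The sample size in 12.3 rests on troponin. The check is mainly textual.

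**1. Who is assigned what**

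| Variable | Planned test (12.2) | Assessor named | Blinded? |
|---|---|---|---|
| cTnI at 24 h | ANCOVA | Laboratory assay (6.3.1) | Set aside in 5.3 as not needing assessment |
| Chest pain | ANOVA | Patient report to investigator or delegate (6.3.1, 6.5) | Set aside in 5.3 |
| ST deviation | ANOVA | Two experts (5.3) | Yes |
| TIMI bleeding, any | Fisher | None named | Not stated |
| TIMI bleeding, major | Fisher | None named | Not stated |

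**2. Which classes are exposed** (2.3)

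- Less exposed: fatal bleeding, intracranial bleeding, and classes fixed by a haemoglobin or haematocrit drop, at least while scheduled tests run (Days 1 to 3).
- More exposed: overt bleeding without a qualifying laboratory drop, and the catch-all minimal item.
- Exposed in a different way: bleeds that qualify because someone intervened, changed study drug, or ordered an unscheduled evaluation. These decisions are made with the arm known, before any form could reach an assessor.

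**3. What blinded classification can change in each test**

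Take the composite to include every TIMI class; 12.2 does not list its components.

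| Decision on a suspected event | Any-bleeding composite | Major bleeding |
|---|---|---|
| Minimal to minor, or the reverse | No change | No change |
| Minor to major, or the reverse | No change | Changes by 1 |
| Counts as a bleed, or does not | Changes by 1 | Changes by 1 only if major |

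Assigning tiers alone would therefore bear on the major-bleeding test only. To bear on both tests, the assessors must also decide whether a suspected event qualifies.

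Scale: 152 / 2 = 76 patients per drug arm, and 1 / 76 = 1.3 percentage points of incidence per event.

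**4. Ascertainment: a separate bias, with assumed figures**

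Assume a true any-bleeding rate of 15% in both arms and unequal recording. Observed rate = true rate × recording probability; the risk ratio is the ratio of recording probabilities.

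- 90% v 70%: 0.15 × 0.90 = 13.5%; 0.15 × 0.70 = 10.5%; RR 1.29. Expected events: 76 × 0.135 = 10.3 v 76 × 0.105 = 8.0.
- 90% v 80%: 13.5% v 12.0%; RR 1.13.

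Exact two-sided Fisher rejection probability with 76 per arm at nominal 5%, by assumed true rate:

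| True rate | 90% v 90% | 90% v 80% | 90% v 70% |
|---|---|---|---|
| 5% | 1.3% | 1.3% | 1.5% |
| 10% | 2.6% | 2.8% | 3.8% |
| 15% | 2.9% | 3.5% | 5.5% |
| 20% | 3.0% | 3.8% | 6.8% |
| 30% | 3.3% | 4.9% | 10.2% |

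The risk ratio is distorted at every rate. The test exceeds its nominal level only when bleeding is fairly common and the recording gap is wide. These figures describe bleeds that were never recorded. Blinded classification of recorded bleeds leaves them unchanged, so they do not measure the benefit of the fix.

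**The case against.** The strongest reply has four parts.

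**The general sentence in 5.3 may already cover bleeding.** It speaks of outcomes without limit, and no section names an unblinded grader. This stands in part: the scope is unclear rather than expressly closed. A reader might infer that the protocol assigns bleeding grading to the treating investigators; it does not say so. But if blinded review was intended, nothing says how masked records reach the assessors or that 12.2 uses their decision. The same edit is needed on either reading.

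**Major bleeding is largely objective.** It rests on intracranial bleeding, a large haemoglobin or haematocrit drop with overt signs, or death. Laboratory tests on Days 1 to 3 and bleeding-directed examinations apply to all patients. This stands, and it confines the concern mostly to the lesser events in the composite.

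**Grading tiers would not move the composite.** Correct if every tier is included, as the third step of the working shows. It is answered only by having the assessors rule on whether an event qualifies.

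**Blinded readers cannot cure detection bias.** Correct. A reader might infer that the two assessors could eliminate bias in the bleeding comparison. The documents do not support that: after discharge detection relies on reports from patients who know their drug, and several criteria are actions already taken with the arm known.

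**Conclusion.** The concern holds in a limited form. The plan formally tests TIMI bleeding in an open-label trial without naming a grader or providing masked review, while it has two blinded assessors whose only express task is ST deviation. The drug comparison on bleeding is therefore open to classification bias, mostly through judgement-based minor and minimal events.

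The size of that bias cannot be estimated from the documents. The risk ratios of 1.29 and 1.13 rest on assumed rates, concern ascertainment only, and are not an estimate of what masked classification would gain.

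The conclusion rests on three readings: that site staff would classify bleeds by default, that the composite spans all TIMI classes, and that the Fisher tests compare the two drugs (12.2 does not name the comparison). Troponin, the sample size of 152 and the efficacy analyses are unaffected. This is a cheap improvement, not a defect that undermines the trial.

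**What to change.** **Section 5.3.** State that the same two blinded assessors decide, for every suspected bleed, both whether it qualifies as a TIMI bleed and its class, with the consensus rule already in place. They work from a bleeding form completed by the site (location, signs, haemoglobin and haematocrit, action taken) with drug name and allocation removed.

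**Section 12.2.** State that both Fisher tests use this adjudicated classification.

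**Limitation to record.** Differential detection and reporting remain, as do criteria that are open-label decisions (intervention, study-drug change, prompted evaluation). Asking the same scheduled bleeding questions in both arms would help with detection but would not remove the problem.

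Site SAE reporting and causality assessment stay as they are. The cost is one CRF page, redaction of a limited number of records and modest assessor time; no new staff or patients are needed.
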